4.2.3.1.1 Definition of Efficacy Endpoints

4.2.3.1.1.1 Overall Response

The overall response will be estimated based on the following: (a) survival (based upon all-cause mortality) through Day 28 post-randomization in subjects with HABP/VABP, (b) clinical response at Day 28 post-randomization for subjects with cIAI and (c) the composite clinical and microbiological response at EFU for subjects with cUTI. Overall response will be determined by summarizing the proportion of subjects who survive through Day 28 post-randomization (HABP/VABP), or have a “favorable” clinical (cIAI) or “favorable” composite microbiological and clinical (cUTI) response.

A favorable response is defined differently for each infection type, and these definitions will be combined to provide an estimate of favorable overall response (See [Table 2](#) for a description of the components of the overall response). The definitions for the relevant response types that contribute to overall response are included in each of the referenced sections describing survival/all-cause mortality assessment (Section 4.2.3.1.1.1.1), clinical response (Section 4.2.3.1.1.1.2) and microbiological response (Section 4.2.3.1.1.1.3). Details regarding determination of microbiological and clinical response (“favorable” or “unfavorable”) in support of evaluation of overall response at Day 28 post-randomization are provided in Section 8.2.

Table 2 Description of Individual Infection Site Responses Supporting Determination of Favorable Overall Response (Primary Endpoint)

Infection Site	Type of Response (Timing)	Favorable Response	Reference (Section/Table #) for Definition of Response
HABP/VABP	Survival/All-Cause Mortality (Day 28)	Survival at Day 28	Section 4.2.3.1.1.1.1
cIAI	Clinical Response (Day 28)	
 • Sustained cure • Cure 	Section 4.2.3.1.1.1.2 Table 5
cUTI	Composite Clinical (EFU) and Microbiological Response (EFU)	Clinical Response: 
 • Sustained cure • Cure Microbiological Response: 
 • Sustained eradication 	Clinical Response: Section 4.2.3.1.1.1.2 Table 5 Microbiological Response: Section 4.2.3.1.1.1.3 Table 8

4.2.3.1.1.1.1 Survival/All-Cause Mortality

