5.2 Trial Treatment(s)

The treatments to be used in this trial are outlined below in [Table 10](#).

Table 10 Trial Treatments

Drug	Dose/Potency ^b	Dose Frequency	Route of Administration	Regimen/Treatment Period ^c	Use
Treatment Group 1 (N = 36) or Treatment Group 3					
Imipenem/cilastatin/relebactam (IMI/REL) ^a	Imipenem: 500 mg Relebactam: 250 mg	Every 6 hours	IV	5 or 7 to 21 days	Experimental
Placebo for CMS (diluent for CMS as directed in the Pharmacy Manual)	N/A	Loading dose followed after 12 hours by maintenance dose every 12 hours	IV	5 or 7 to 21 days	Placebo-control
Treatment Group 2 (N = 18)					
Colistin as colistimethate sodium (CMS)	Total maximum daily maintenance dose: 300 mg CBA ^d	Loading dose followed after 12 hours by maintenance dose every 12 hours	IV	5 or 7 to 21 days	Active-comparator
Imipenem/cilastatin (IMI)	Imipenem: 500 mg	Every 6 hours	IV	5 or 7 to 21 days	Active-comparator
CBA: Colistin base activity (300 mg CBA corresponds to approximately 720 mg CMS or ~9 million IU) ^a IMI/REL will be provided combined in a single vial. ^b Adjustments to dosage of IMI/REL, IMI and CMS may be required. Dose adjustment for IMI/REL and IMI are required for subjects with renal insufficiency (Reference Table 11 in Section 5.2.1.1). Dose adjustment for CMS dose in subjects with renal insufficiency is also required (Reference Table 12 in Section 5.2.1.1). ^c IV study therapy should be administered for a minimum of 120 hours (5 full days) for subjects with cIAI or cUTI or 168 hours (7 full days) for subjects with HABP/VABP. The corresponding number of doses required is described in Section 7.1.5.2. The total duration of IV study therapy should not exceed 21 days. Duration of study therapy longer than 21 days must be approved the Sponsor. ^d Subjects who require a loading dose of CMS (Reference Table 12 in Section 5.2.1.1) will receive >300 mg CBA during the first 24 hours of study therapy.					

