8.2.4 Analysis Populations

8.2.4.1 Efficacy Analysis Populations

The microbiological modified Intention to Treat (mMITT) population will serve as the primary population for efficacy analyses in this study. The mMITT population is defined as all randomized subjects who receive at least one dose of each study drug within a given IV study therapy regimen, and who have a baseline bacterial pathogen meeting inclusion criterion #3. In the case of a polymicrobial infection, at least one pathogen must satisfy the requirements of inclusion criterion #3, and all pathogens identified at the baseline time point must be susceptible to both IMI/REL and colistin. Subjects will be included in the treatment group to which they are randomized for the analysis of efficacy data using the mMITT population.

The per-protocol (PP) population will serve as the secondary population for the primary efficacy endpoint (proportion of subjects with a favorable overall response as assessed for each of the three infection types). The PP population is a subset of the mMITT population who also meet the following criteria:

1. Meet important diagnostic criteria for entry into the study,

2. Have no significant deviation from the protocol that could impact the assessment of efficacy, and
3. Receive the minimum duration of IV study therapy as detailed in Section 5.2

The final exclusion criteria and list of patients who will be excluded from the PP population will be documented prior to unblinding.

Details on the approach to handling missing data are provided in Section 8.2.5 (Statistical Methods).

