8.2.5 Statistical Methods

8.2.5.1 Statistical Methods for Efficacy Analyses

This is an estimation study; no formal statistical testing will be performed for the efficacy endpoints. All of the efficacy endpoints in this study are binary. Within-group 95% confidence intervals for these endpoints will be calculated using the Agresti & Coull method. In addition, between-group 90% confidence intervals for the primary and key secondary endpoints will be calculated using the stratified Miettinen and Nurminen method [78], an unconditional, asymptotic method. The between-group estimates will be stratified by infection type where appropriate.

Missing Values

Any subject missing an evaluation for a specific endpoint (clinical, microbiological or overall response) at any particular visit will be generally considered as being “indeterminate” for that endpoint in the mMITT population. The following are exceptions to this rule:

- Subjects discontinuing IV study therapy due to lack of efficacy (e.g., withdrawals with subsequent non-study antibiotic therapy) will be considered as “failures” with respect to clinical response at the time of discontinuation and all subsequent time points.
- Subjects discontinuing IV study therapy due to lack of efficacy will be presumed to have persistence for the microbiological response at the time of discontinuation and all subsequent time points.

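### The per-protocol minimum-duration rule has no exception for early death or lack-of-efficacy stops, so some failures on the primary endpoint drop out of its only secondary analysis population

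*Combined protocol and SAP*

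**What the plan says.** Section 8.2.4.1 gives the PP population a defined role: "The per-protocol (PP) population will serve as the secondary population for the primary efficacy endpoint". It is a subset of mMITT with three further conditions: diagnostic criteria met, no significant deviation bearing on efficacy, and "Receive the minimum duration of IV study therapy as detailed in Section 5.2".

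The duration is in footnote c of Table 10 in Section 5.2: "for a minimum of 120 hours (5 full days) for subjects with cIAI or cUTI or 168 hours (7 full days"), the second figure being for HABP/VABP.

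The primary endpoint differs by stratum (Section 4.2.3.1.1 and Table 2):
- **HABP/VABP:** "survival (based upon all-cause mortality) through Day 28 post-randomization in subjects with HABP/VABP".
- **cIAI:** "clinical response at Day 28 post-randomization for subjects with cIAI".
- **cUTI:** clinical and microbiological response combined, at the early follow-up visit.

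In mMITT, Section 8.2.5.1 provides that "Subjects discontinuing IV study therapy due to lack of efficacy" count as clinical failures and as microbiological persistence from that time on. Table 16 sets missing to failure for the primary endpoint.

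After the three PP conditions, Section 8.2.4.1 adds: "The final exclusion criteria and list of patients who will be excluded from the PP population will be documented prior to unblinding". Section 8.0 says that no separate SAP will be issued.

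**The concern.** The third condition selects on something that happens after randomization and is bound up with the outcome. A pneumonia subject who dies on Day 4 is an endpoint event in mMITT and is absent from PP. A cIAI or cUTI subject taken off study drug on Day 3 because it is not working is a failure in mMITT and is also absent from PP.

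This is not ordinary handling of deviations, which the second condition already covers. Section 5.8 requires study drug to be stopped for several events, so a subject managed exactly as the protocol directs can be excluded.

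PP is the only other population named for the primary endpoint. A reader will take agreement between PP and mMITT as reassurance, and disagreement as information. Neither reading is safe if PP has lost part of the failures, especially with 10 and 5 subjects per arm in each stratum.

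**Working it through.** **Inputs.** Planned mMITT sizes are 30 (Group 1) and 15 (Group 2), or 10 and 5 per stratum (Section 8.2.7). The interval method is Agresti & Coull at 95% (Section 8.2.5.1). The numbers of early exits are not in the documents and are assumptions, varied below.

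**Reproducing the plan's figures.** The interval is p̃ ± z√(p̃(1−p̃)/ñ), with ñ = n + z² and p̃ = (x + z²/2)/ñ. For 18/30, ñ = 33.84 and p̃ = 0.5886, giving 0.5886 ± 0.1658, or 42.3% to 75.4%, as in Table 18. The rows 9/15 (35.7, 80.2), 7/10 (39.2, 89.7) and 21/30 (52.0, 83.5) also reproduce. One of the 16 rows does not: 4/10 prints an upper limit of 66.8 against 68.8 computed. It is not used here.

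**Formula.** Let x of n be favourable in mMITT. Criterion 3 removes k unfavourable and s favourable subjects:

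PP rate = (x − s)/(n − k − s).

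This exceeds x/n when n(x − s) > x(n − k − s), which reduces to k/(n − x) > s/x. PP is inflated when the share of failures removed exceeds the share of successes removed.

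**Who is in k.** Every death before the minimum duration: it is not survival for HABP/VABP, and it cannot be a cure at Day 28 (cIAI) or at early follow-up (cUTI). Also cIAI/cUTI lack-of-efficacy stops, by the Section 8.2.5.1 rule.

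**Who is in s.** HABP/VABP subjects who stop early for any reason and are alive at Day 28, because survival alone is the favourable outcome in that stratum.

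**Only failures removed (s = 0).**
- 7/10 = 70%; k = 1 gives 7/9 = 78%; k = 2 gives 7/8 = 88%.
- 21/30 = 70% (52.0, 83.5); k = 4 gives 21/26 = 81% (61.7, 92.0).
- 3/5 = 60%; k = 1 gives 3/4 = 75%.

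**Survivors removed in HABP/VABP, starting from 7/10.**
- k = 0, s = 1: 6/9 = 67%, below 70%.
- k = 1, s = 1: 6/8 = 75%.
- k = 1, s = 3: 4/6 = 67%, below 70%.

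**Between arms.** Take 60% in both arms in mMITT (18/30 and 9/15), with s = 0:

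| k, Group 1 | k, Group 2 | PP, Group 1 | PP, Group 2 | Difference (points) |
|---|---|---|---|---|
| 2 | 1 | 64.3% | 64.3% | 0.0 |
| 3 | 3 | 66.7% | 75.0% | −8.3 |
| 0 | 3 | 60.0% | 75.0% | −15.0 |
| 4 | 0 | 69.2% | 60.0% | +9.2 |

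The true mMITT difference is zero in every row. Removal in proportion to arm size leaves it at zero; unequal removal does not, and the sign follows the arm that loses the larger share of its failures.

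**The case against.** The strongest case against the point is that little depends on it and that the plan already contains safeguards. mMITT is primary and keeps these subjects. Efficacy is estimation only. Day 28 all-cause mortality is a key secondary endpoint in mMITT, so early deaths there are counted. Section 8.1.1 promises to assess the effect of differences in therapy duration, Section 8.2.5.3 displays reasons for discontinuation, and the PP exclusions are still to be finalized before unblinding. All of this stands, and it limits the point to a secondary analysis. It does not supply the exception: permission to settle the criteria later allows a repair but does not make one, and criterion 3 as written excludes these subjects.

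Four stronger readings are tempting, and the documents do not support them.
- **PP response is inflated in both arms, and most in the arm with more toxicity stops.** In HABP/VABP, early-stopping survivors are removed as well, which pulls the rate down.
- **Everyone who fails early is excluded.** Only those who die or stop before the minimum are. A subject rated as persistence or progression on Day 3 who continues to Day 5 or 7 stays in PP.
- **PP undoes the mMITT failure rule in every stratum.** That rule covers clinical and microbiological response. It does not govern survival, so a HABP/VABP subject who stops for lack of efficacy and lives is a success in mMITT.
- **Early exits are expected from the cited 16–60% mortality and 0–30% colistin nephrotoxicity.** The first (Section 4.2.1) is overall mortality in critically ill patients, not death before Day 5 or 7. The second (Section 4.1.3) is an incidence of mostly mild, reversible events, not a rate of stopping. This trial also excludes APACHE II scores above 30 from the randomized groups and plans one third cUTI.

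**Conclusion.** The point holds in a limited form. Criterion 3 makes entry to PP depend on a post-randomization event tied to the outcome. Early deaths in any stratum, and early lack-of-efficacy stops in cIAI and cUTI, are lost as failures, and each such loss raises the PP rate. The removal of early-stopping HABP/VABP survivors works the other way, so the net direction is not established.

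The size cannot be derived from the documents. The illustrations, 8 points for one early death in a stratum of 10 and 11 points for four early failures in 30, rest on assumed counts and on no early-stopping successes. They show sensitivity at these sample sizes; they are not a forecast. The consequence is that PP, as defined, is weak corroboration of the primary result. The mMITT estimate itself is not affected.

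**What to change.** Add one sentence to Section 8.2.4.1: criterion 3 does not exclude subjects who die, or who discontinue IV study therapy for lack of efficacy, before the minimum duration; they remain in PP and are scored by the same infection-type definition as in mMITT. That means Day 28 survival status for HABP/VABP, and failure or persistence for cIAI and cUTI. Scoring them identically keeps the endpoint the same in both populations, so a HABP/VABP subject who stops for lack of efficacy and survives remains a success.

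No minimum exposure should be attached to this exception. The 48-hour figure in Table 7, footnote g, concerns which urine culture may stand in for a missing end-of-therapy culture, and a 48-hour floor would again drop the earliest deaths.

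The change concerns analysis only and alters no treatment rule. Its costs are that PP rates may be somewhat less favourable and that PP will include some subjects with short exposure. Early stops for toxicity would still be excluded, so PP remains a population selected on treatment received and should be reported as such, with the number and reasons of criterion 3 exclusions by arm and stratum.

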8.2.4.2 Safety Analysis Populations

The ASaT population will be used for the analysis of safety data in this study. The ASaT population consists of all subjects who received at least one dose of IV study therapy. The ASaT includes non-randomized subjects in Treatment Group 3 (IMI/REL), as well as randomized subjects in Treatment Group 1 (IMI/REL) and Treatment Group 2 (CMS + IMI). Subjects will be included in the therapy group corresponding to the study therapy they actually received for the analysis of safety data using the ASaT population. Subjects who are administered incorrect study therapy for the entire treatment period will be included in the therapy group corresponding to the study therapy actually received.

At least one laboratory or vital sign measurement obtained subsequent to at least one dose of IV study therapy is required for inclusion in the analysis of each specific parameter. To assess change from baseline, a baseline measurement is also required.

Since the assessment of treatment-emergent nephrotoxicity requires serum creatinine measurements at baseline and after at least one dose of IV study therapy, subjects who have missing data at either of these time points will be excluded from the summaries/analyses of this endpoint.

Details on the approach to handling missing data for safety analyses are provided in Section 8.2.5 (Statistical Methods).

8.2.5 Statistical Methods

8.2.5.1 Statistical Methods for Efficacy Analyses

This is an estimation study; no formal statistical testing will be performed for the efficacy endpoints. All of the efficacy endpoints in this study are binary. Within-group 95% confidence intervals for these endpoints will be calculated using the Agresti & Coull method. In addition, between-group 90% confidence intervals for the primary and key secondary endpoints will be calculated using the stratified Miettinen and Nurminen method [78], an unconditional, asymptotic method. The between-group estimates will be stratified by infection type where appropriate.

Missing Values

Any subject missing an evaluation for a specific endpoint (clinical, microbiological or overall response) at any particular visit will be generally considered as being “indeterminate” for that endpoint in the mMITT population. The following are exceptions to this rule:

- Subjects discontinuing IV study therapy due to lack of efficacy (e.g., withdrawals with subsequent non-study antibiotic therapy) will be considered as “failures” with respect to clinical response at the time of discontinuation and all subsequent time points.
- Subjects discontinuing IV study therapy due to lack of efficacy will be presumed to have persistence for the microbiological response at the time of discontinuation and all subsequent time points.

8.2.5.2 Statistical Methods for Safety Analyses

Safety and tolerability will be assessed by clinical review of all relevant parameters including adverse experiences (AEs), laboratory tests, and vital signs.

Any analysis of safety data that involves a comparison of IMI/REL to CMS + IMI will be restricted to Treatment Group 1 and Treatment Group 2 (the randomized treatment groups). Data from Treatment Group 3 will be summarized separately using descriptive statistics.

Due to concern for potential renal toxicity of colistin, Treatment Group 1 (IMI/REL) and Treatment Group 2 (CMS + IMI) will be compared with respect to the proportion of subjects who experience treatment-emergent nephrotoxicity using the two-sided p-value from the Fisher Exact Test.

Other safety parameters will follow a tiered approach (Table 17). The tiers differ with respect to the analyses that will be performed. Safety parameters or adverse experiences of special interest that are identified a priori constitute “Tier 1” safety endpoints that will be subject to inferential testing for statistical significance with p-values and 95% confidence intervals provided for between-group comparisons. All other safety parameters will be considered Tier 2 or Tier 3. Tier 2 parameters will be assessed via point estimates with 95% confidence intervals provided for between-group comparisons; only point estimates by treatment group are provided for Tier 3 safety parameters. P-values (Tier 1 only) and 95% confidence intervals (Tier 1 and Tier 2) will be provided for between-treatment differences in the percentage of subjects with events; these analyses will be performed using the (unstratified) Miettinen and Nurminen method [78], an unconditional, asymptotic method (with the exception of treatment-emergent nephrotoxicity as described above).

Adverse experiences (specific terms as well as system organ class terms) and other safety parameters that are not pre-specified as Tier-1 endpoints will be classified as belonging to “Tier 2” or “Tier 3”, based on the number of events observed. Membership in Tier 2 requires that at least 4 subjects in at least one treatment group exhibit the event; all other adverse experiences and safety parameter will belong to Tier 3.

The threshold of at least 4 events was chosen because the 95% confidence interval for the between-group difference in percent incidence will include zero when each treatment group has less than 4 events and thus would add little to the interpretation of potentially meaningful differences. Because many 95% confidence intervals may be provided without adjustment for multiplicity, the confidence intervals should be regarded as a helpful descriptive measure to be used in review, not a formal method for assessing the statistical significance of the between-group differences in adverse experiences and predefined limits of change.

Continuous measures such as changes from baseline in laboratory parameters that are not pre-specified as Tier-1 endpoints will be considered Tier 3 safety parameters. Summary statistics for baseline, on-treatment, and change from baseline values will be provided by treatment group in table format. Laboratory values from the Central Laboratory will be used for these analyses when available.

Table 17 Analysis Strategy for Safety Parameters

Safety Tier	Safety Endpoint [†]	p-Value	95% CI for Treatment Comparison	Descriptive Statistics
Tier 1	treatment-emergent nephrotoxicity	X	X	X
	elevated AST or ALT ≥ 3 X ULN and elevated total bilirubin ≥ 2 X ULN and alkaline phosphatase < 2 X ULN	X	X	X
	A confirmed elevated AST or ALT ≥ 5 X ULN	X	X	X
Tier 2	Any AE		X	X
	Any Serious AE		X	X
	Any Drug-Related AE		X	X
	Any Serious and Drug-Related AE		X	X
	Discontinuation due to AE		X	X
	Discontinuation due to Drug-Related AE		X	X
	Specific AEs, SOC [‡] , or PDLCs [‡] (incidence ≥ 4 of subjects in one of the treatment groups)		X	X
Tier 3	Specific AEs, SOC [‡] or PDLCs [‡] (incidence < 4 of subjects in all of the treatment groups)			X
	Change from Baseline Results (Labs, ECGs, Vital Signs)			X

[†] Adverse Experience references refer to both Clinical and Laboratory AEs.

[‡] Includes only those endpoints not pre-specified as Tier 1 or not already pre-specified as Tier 2 endpoints.

Note: SOC=System Organ Class; PDLC=Pre-Defined Limit of Change; X = results will be provided.

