4.2.3.2 Safety Endpoints

In support of the primary objective to evaluate the safety and tolerability profile of IMI/REL, the safety and tolerability of IMI/REL (as well as the safety of the comparator, CMS + IMI) will be assessed by clinical evaluation of adverse experiences and inspection of other study parameters including vital signs, physical examinations, and standard laboratory safety tests at time points specified in the Trial Flow Chart. Adverse experiences are graded and recorded according to Section 7.2. Subjects may be asked to return for unscheduled visits in order to perform additional safety monitoring.

In addition, due to concern for potential renal toxicity of colistin, the relative rates of nephrotoxicity of IMI/REL and CMS + IMI will be evaluated as a secondary endpoint in this study. Evaluation of potential nephrotoxicity will be performed based on laboratory test results from blood samples.

As discussed in Section 4.1.3, the reported incidence of nephrotoxicity associated with colistin administration is variable. In addition to the lack of a standard dosing algorithm for colistin, a major difficulty in determining the true incidence of nephrotoxicity associated with intravenous colistin therapy is the absence of a standardized and consistently applied definition of nephrotoxicity. In this study, the definition of nephrotoxicity will be based on alterations in baseline serum creatinine and renal function as described in Table 9. Serum creatinine level as well as creatinine clearance are commonly used in clinical practice to measure renal function. In addition, there is evidence that changes in serum creatinine are associated with an increase in short-term morbidity and even mortality, thus making serum creatinine an appropriate marker for measuring acute kidney injury [73]. Changes in

creatinine and renal function have frequently been used in the literature to describe colistin-associated nephrotoxicity [13, 17, 21-23, 26, 74, 75, 76].

Table 9 Criteria for Defining Nephrotoxicity

Baseline Renal Function Category	Baseline Serum Creatinine Level	Definition of Nephrotoxicity
Normal	<1.2 mg/dL	Doubling of serum creatinine (to >1.2 mg/dL), OR Reduction in the calculated creatinine clearance ^a (CL _{Cr}) of ≥50%.
Pre-Existing Renal Dysfunction	≥1.2 mg/dL	Increase in serum creatinine by ≥1 mg/dL, OR Reduction from baseline in calculated CL _{Cr} ^a of ≥20%, OR Need for RRT.

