5.4 Stratification

Randomization will be stratified according to the following infection types:

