8.2.7 Sample Size and Power Calculations

This study will randomize approximately 54 subjects in a 2:1 ratio into 2 treatment groups (Group 1: IMI/REL and Group 2: CMS + IMI) in order to obtain a minimum of 45 subjects (15 per infection type) who meet the criteria for inclusion in the microbiological modified intent-to-treat (mMITT) population. An additional 5 to 10 subjects with imipenem-resistant and colistin-resistant bacterial infection will be enrolled into a third non-randomized, open-label treatment group (Group 3: IMI/REL). This is an estimation study; no formal statistical testing will be performed for the efficacy endpoints. The sample sizes planned for the study arise from logistic feasibility and are not driven by statistical considerations.

[Table 18](#) displays two-sided 95% confidence intervals for the proportion of subjects with a favorable overall response under varying assumptions for the number of successes in Treatment Group 1 (IMI/REL) and Treatment Group 2 (CMS + IMI). Estimates are provided for:

- N=5 (number of Treatment Group 2 subjects in each infection type),
- N=10 (number of Treatment Group 1 subjects in each infection type),
- N=15 (number of Treatment Group 2 subjects combined over all infection types),
- N=30 (number of Treatment Group 1 subjects combined over all infection types).

NOTE: These intervals are not symmetric around the point estimate.

Table 18 Two-Sided 95% Confidence Intervals for Favorable Overall Response

Number of subjects in population	Observed Number with Favorable overall response	(%)	Two-Sided 95% Confidence Interval ^a
5	2	40.0%	(11.6, 77.1)
	3	60.0%	(22.9, 88.4)
	4	80.0%	(36.0, 98.0)
10	4	40.0%	(16.7, 66.8)
	5	50.0%	(23.7, 76.3)
	6	60.0%	(31.2, 83.3)
	7	70.0%	(39.2, 89.7)
	8	80.0%	(47.9, 95.4)
15	6	40%	(19.8, 64.3)
	9	60%	(35.7, 80.2)
	12	80%	(54.0, 93.7)
30	12	40.0%	(24.6, 57.7)
	15	50.0%	(33.2, 66.8)
	18	60.0%	(42.3, 75.4)
	21	70.0%	(52.0, 83.5)
	24	80.0%	(62.3, 90.9)

^a 95% confidence intervals calculated with the Agresti & Coull method.

Table 19 displays several possible study outcomes for the comparison of Treatment Group 1 (IMI/REL) to Treatment Group 2 (CMS + IMI) with regard to the difference in the proportion of subjects who experience treatment-emergent nephrotoxicity. This table shows that a difference between the groups of about 3 events favoring Treatment Group 1 (IMI/REL) would be associated with a two-sided p-value that is less than 0.05.

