		# with Nephrotoxicity in CMS+IMI group (N=15)						
		0	1(6.7%)	2 (13.3%)	3 (20%)	4 (26.7%)	5 (33.3%)	6 (40%)
# with Nephrotoxicity in IMI/REL group (N=30)	0	>0.5	0.333	0.106	0.032	0.009	0.002	<0.001
	1 (3.3%)	>0.5	>0.5	>0.5	0.101	0.036	0.012	0.003
	2 (6.7%)	>0.5	>0.5	>0.5	0.315	0.085	0.032	0.011
	3 (10%)	>0.5	>0.5	>0.5	>0.5	0.199	0.095	0.042

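### The pooled nephrotoxicity test ignores a baseline creatinine category that sets two very different event thresholds; a category-stratified estimate should be added beside the Fisher test.

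*Combined protocol and SAP*

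**What the plan says.** Table 9 (Section 4.2.3.2) splits subjects at a baseline creatinine of 1.2 mg/dL. In the lower category an event is "Doubling of serum creatinine (to >1.2 mg/dL") or a fall of at least 50% in calculated clearance. In the upper category it is "Increase in serum creatinine by ≥1 mg/dL, OR Reduction from baseline in calculated" clearance of at least 20%, or renal replacement therapy. Clearance comes from the Cockcroft-Gault equation in Section 5.2.1.1.

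Section 5.4 states: "Randomization will be stratified according to the following infection types". Renal function is not a stratum. Entry criteria exclude only clearance below 15 mL/min and dialysis, so both categories can enrol.

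Nephrotoxicity is a key secondary objective (Section 3.2.1) and a Tier 1 safety event (Section 8.2.3.2). Under Section 8.2.5.2 the two randomised arms "will be compared with respect to the proportion of subjects who experience treatment-emergent nephrotoxicity using the two-sided p-value from the Fisher Exact Test", pooled over both categories; Table 16 names the same test. The subgroup list in Section 8.2.8 covers overall response only and has no renal factor. Table 17 promises a 95% CI for the nephrotoxicity comparison, but Section 8.2.5.2 exempts this endpoint from the Miettinen-Nurminen method, so no between-group interval method is named for it.

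**The concern.** The category decides how easily a subject counts as an event, whatever the drug does. In a trial of about 36 versus 18 subjects, the category can fall unevenly between arms by chance. If more upper-category subjects land in the colistin arm, that arm is expected to show more events with no drug difference. If they land in the IMI/REL arm, a real colistin effect can be hidden. The pooled two-by-two table cannot tell these situations apart.

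The plan treats a parallel problem differently. The primary endpoint also pools different definitions, by infection type, and there both the randomisation and the between-group interval are stratified (Sections 5.4 and 8.2.5.1). What is at stake is how the main between-group safety comparison is read, since Section 8.2.7 says that a gap of about three events "would be associated with a two-sided p-value that is less than 0.05".

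**Working it through.** **1. The plan's own figure.** Table 19 uses 30 IMI/REL and 15 CMS+IMI subjects. Two-sided Fisher p-values for IMI/REL versus CMS+IMI events of 0 v 3, 1 v 4, 2 v 5 and 3 v 6 come out at 0.032, 0.036, 0.032 and 0.042, as printed. Overall 25 of the 28 cells reproduce. The other three (1 v 2: 0.254; 2 v 4: 0.157; 3 v 3: 0.384) differ from print without crossing 0.05, and do not bear on this point.

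**2. The threshold gap.** At fixed age and weight, Cockcroft-Gault clearance is proportional to 1/creatinine. A 20% fall therefore means creatinine × 1/0.8 = × 1.25, and a 50% fall means × 2. A subject at 1.19 mg/dL must reach 2.38; a subject at 1.20 need only reach 1.50. The 1 mg/dL rise is the easier criterion only when b + 1 < 1.25b, i.e. baseline above 4 mg/dL.

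**3. Assumptions.** The documents give an overall colistin rate of 0 to 30% (Section 4.1.3), with no category shares or category-specific rates. Assumed here: one third of subjects in the upper category; no drug effect; event rates (lower/upper) of 5/30%, 5/40% and 10/40%.

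**4. Shift in the crude difference.** Expected shift = gap in category share × (upper rate − lower rate). A 20-point gap gives 0.20 × 0.25 to 0.20 × 0.35 = 5 to 7 points, or 0.75 to 1.05 events in 15. A 30-point gap gives 7.5 to 10.5 points, or 1.1 to 1.6 events. The sign follows the direction of the imbalance.

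**5. Conditional rejection rate of pooled Fisher.** Exact enumeration at 30:15 with 15 of 45 subjects in the upper category: binomial events within category, hypergeometric category split, rejection at p ≤ 0.05.

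| Upper category, CMS+IMI v IMI/REL | Gap (points) | Chance of a gap at least this large, CMS+IMI heavier | 5/30% | 5/40% | 10/40% |
|---|---|---|---|---|---|
| 5/15 v 10/30 | 0 | – | 1.8% | 1.5% | 2.1% |
| 7/15 v 8/30 | 20 | 15.7% | 4.8% | 5.2% | 4.4% |
| 8/15 v 7/30 | 30 | 4.8% | 7.7% | 9.6% | 7.1% |
| 10/15 v 5/30 | 50 | 0.1% | 17.3% | 25.3% | 16.4% |

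An exact test stratified by category stays at 2.2 to 2.9% on all four splits. At 36:18 with 18 of 54 in the upper category, a gap of 20 points or more towards CMS+IMI has probability 6.4%, and the pooled rate given that is 7.8 to 10.3%.

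**6. Overall rejection rate.** Averaged over all allocations, pooled Fisher rejects 2.6 to 3.1% at 30:15 and 3.1 to 3.5% at 36:18. With equal rates of 5/5% it rejects 1.0% at 30:15 whatever the split.

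**7. One data set, three splits.** Take 4/15 versus 1/30 events, all in the upper category. Pooled p = 0.036 in every case. In the stratified exact test only the upper category is informative, with 5 events among 15 subjects and C(15,5) = 3003 arrangements. The sum runs over outcomes no more probable than the one observed.
- 5/15 v 10/30: (50 + 1)/3003 = 0.017.
- 8/15 v 7/30: (490 + 56 + 280 + 21)/3003 = 0.28.
- 10/15 v 5/30: (1050 + 252 + 450 + 50 + 1)/3003 = 0.60.

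**8. Precision.** Null variance of the crude difference scales with p̄(1 − p̄), and of the stratified difference roughly with the share-weighted mean of p(1 − p). For 5/30%: 0.1156 against 0.1017, 12% less. For 5/40%: 0.1389 against 0.1117, 20% less. For 10/40%: 0.1600 against 0.1400, 12.5% less. Simulation with a 35% share and rates of 2 to 5% versus 30 to 45% gave 16 to 22%.

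**The case against.** The strongest reply is that nothing is broken. Randomisation makes the crude difference unbiased and Fisher holds its level; across 42 null settings its simulated size was 0.5 to 3.6%. A reader might infer from the conditional figures that type I error is lost, or that the arm with more upper-category subjects must show more events. The documents support neither: step 6 shows overall control, and the shift is only in expectation, given an imbalance.

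The effect is also modest. At 36:18 a gap of 20 points or more in either direction arises in about 13% of trials and is worth roughly one event in 18. Every size rests on assumed shares and rates. The power effect of stratifying depends on the scenario (−0.6 to +5.7 points over an unstratified score test in eight settings). All of this stands, and it limits the weight of the point.

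A reader might further infer that Fisher should be replaced. It should not on this ground. The plan chose an exact test for this endpoint deliberately and built Table 19 on it, and the category argument supports stratifying, not a move to an asymptotic test.

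Two replies carry less weight. Baseline creatinine summaries by arm (Sections 8.2.5.2 and 8.2.5.3) may reveal an imbalance but do not correct for it, and an adjustment chosen after unblinding would be post hoc. That the sample size is not statistically driven does not matter either, because the plan still specifies a p-value and an interval for this comparison.

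**Conclusion.** The gap is certain: two event definitions, one pooled comparison, and no balancing, stratification or reporting by the category that separates them. The consequence is conditional bias and some lost precision, not an invalid test. Under the stated assumptions, a 30-point excess of upper-category subjects in the colistin arm (about a 5% chance of that or worse at 30:15) raises the false-positive rate from about 2% to 7 to 10%. An excess in the other arm pulls the difference the other way and can mask toxicity. If event rates were equal in the two categories there would be no distortion. That would be surprising when one category needs a 25% creatinine rise and the other a doubling, but the documents do not settle it. Confidence is high on the structure and moderate on the size. The point is a cheap improvement, and it asks for no change to Table 9.

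**What to change.** In Section 8.2.5.2 and Tables 16 and 17, keep the two-sided Fisher exact test as planned and pre-specify:

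1. Nephrotoxicity counts and denominators by arm within each Table 9 baseline category (below 1.2 mg/dL; 1.2 mg/dL or more).
2. A between-group difference with 95% CI stratified by that category, using the stratified Miettinen-Nurminen method already named in Section 8.2.5.1. This also supplies the interval that Table 17 promises without a method.
3. An exact p-value stratified by category, labelled as supportive of the Fisher result.

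Baseline creatinine is already required for this endpoint (Section 8.2.4.2), so no extra subjects, samples or visits are needed. The cost is SAP wording and one stratification variable. The downsides are small strata, slightly more analysis work, and a second p-value whose supportive status must be stated in advance.
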